1. Explore whether a hip-focused treatment leads to reduced disability and improved physical function when compared to a low back-focused treatment in an at-risk hip-spine subgroup (i.e. those with both hip pain and weakness, in addition to low back pain).
2. Determine what contributes to improvements in disability and physical function in this at-risk hip-spine subgroup.

6. PROCEDURES Describe all procedures involving human subjects for this protocol. Include copies of all surveys and research measures.

Study Participants.

Participants with moderately intense (LBP rated at least 4/10), chronic LBP (pain of at least 3 months) that impacts daily activities with concurrent hip pain and hip weakness will be recruited from newspaper and online advertisements, as well as from databases of former study participants who have agreed to be contacted for future studies. The sample will be recruited from one of three areas in this multi-site clinical trial: Newark, DE and surrounding communities, Pittsburgh, PA and surrounding communities and Durham, NC and surrounding communities.

Design and Randomization Plan.

In total, 180 participants meeting the inclusion/exclusion criteria will be randomly assigned into one of two intervention groups: (1) spine treatment supplemented with a hip-focused manual therapy and hip-focused exercise intervention, or (2) spine-focused rehabilitation with stationary cycling. We will use statistical software to generate a randomization plan that ensures by the end of the study that an equal number of participants are randomly assigned to each of the two treatment conditions. We will perform randomization separately in men and women given the reported sex differences in pain conditions among older adults²⁵, this approach will ensure equal randomization of men and women into both randomization groups. The treatment assignments will be uploaded into the web-based data entry application for the study. A participant's study allocation will be revealed to approved study personnel (i.e. not physical therapy testers) once all eligibility criteria have been entered and eligibility is confirmed.

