Quebec score and gait speed will be used to test our specific hypotheses about short-term (immediately post-treatment) and longer-term (6-months post-randomization) changes in disability and pain severity. We will use linear mixed models with time (baseline, 8 weeks and 6 months) and the group*time interaction as fixed effects while controlling for repeated measures using an unstructured correlation matrix between time points. The effect of time will be treated as categorical. No main effect for treatment is included as the baseline means are assumed and constrained to be equal due to randomization. We will also control for site and sex as fixed effects since these are stratification factors in the randomization. We will use linear contrasts to test HIP+ versus SFR at 8 weeks and 6 months (Aim 1). GLMM assumptions include homoscedasticity, normality, and linearity using standard graphical methods, the Shapiro-Wilk test, and Box-Cox test respectively. If model assumptions are violated, we will consider transformations (e.g. Box-Cox method) that can be applied but maintain interpretability. We will test the secondary outcome measures related to Aim 1 in the same fashion to identify which outcomes should be considered in future trials.

The rates of individual adverse events and serious adverse events that occur >10% and adverse events classified by organ system and relatedness will be calculated for each group and compared using Chi-square or Fisher's exact tests.

Aim 2: Hypothesis. Reductions in hip joint pain, increases in hip strength and increases in functional self-efficacy will be associated with improvements in LBP-related disability and physical function.

Two sets of regression analyses will be used to determine the degree to which changes in hip pain, hip strength and functional self-efficacy explain changes in LBP-related disability and physical

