function, as measured by change in Quebec score and gait speed, respectively. The first set of models will examine the change from baseline to immediately post-treatment (8 weeks) and the second set from immediately post-treatment to 6 month follow up for Quebec scores. The second set will do the same but for changes in gait speed. Sequential Multiple Linear Regression Models will be used to test if predictors of interest are related to the outcomes after adjusting for potential covariates. This can be evaluated by testing the ΔR^2 that results from adding subsequent blocks of predictors to each model. If the block is significant, then the tests of the individual predictors will be examined. In the first block will be covariates that are potential confounders (i.e. age and sex) as well as the baseline values of hip pain, hip strength and self-efficacy. [Internal rotation strength relative to body mass, will be chosen as a representative hip strength measure, based on strength of association in our original data]. In the second block of each model will be the treatment group and change values for the predictors of hip pain, hip strength and self-efficacy. All assumptions for models will be tested: multicollinearity by examining the Variance Inflation Factor and Condition Index; normality using Shapiro-Wilk test; Homoscedasticity using the Breusch-Pagan test; and Linearity using the Box-Cox test. If assumptions are violated, transformations suggested by a Box-Cox test will be employed; if that fails Generalized Linear Models will be used.

Additionally, as an exploratory analysis a path analysis will be used to test if the relationship between baseline hip measures (pain, strength, and self-efficacy) and changes in disability and function are mediated by changes in the hip measures. Model fit will be examined using the chi-square model fit test, and standard fit indices (Root Mean Square Error of Approximation (RMSEA), Standardized Root Mean Residual (SRMR), Comparative Fit Index (CFI), and the Tucker-Lewis Index (TLI)) and to address the research question the significance of the indirect effect will be examined. It is likely that this analysis will be underpowered given the number of variables included. However, the analysis will provide a basis for further hypothesis generation and inform the follow-up study.

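### Aim 2 asks what contributes to improvement, but its regressions, read naturally, relate hip and outcome changes over the same window and omit start-of-window values, so they support association only

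*Combined protocol and SAP*

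**What the plan says.** The wording of Aim 2 changes between sections.

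- Section 5 (Research Abstract), specific aim 2: "Determine what contributes to improvements in disability and physical function in this at-risk hip-spine subgroup".
- Section 10 (Data), Statistical Analysis, Aim 2 hypothesis: reductions in hip pain and gains in hip strength and self-efficacy "will be associated with improvements in LBP-related disability and physical function".
- Same section, purpose of the regressions: the degree to which "changes in hip pain, hip strength and functional self-efficacy explain changes in LBP-related disability and physical" function.

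The models are sequential linear regressions. For the Quebec score they examine "change from baseline to immediately post-treatment (8 weeks) and the second set from immediately post-treatment to 6 month follow up for Quebec scores". For gait speed, "The second set will do the same but for changes in gait speed". Block 1 holds "age and sex) as well as the baseline values of hip pain, hip strength and self-efficacy". Block 2 holds "the treatment group and change values for the predictors of hip pain, hip strength and self-efficacy". The interval of those hip changes is not stated. The plan contains no lagged model, no reverse-direction model and no statement of causal assumptions.

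An exploratory path analysis follows. It takes baseline hip measures as the exposure and hip changes as the mediator, and gives no interval for either change.

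**The concern.** If hip change and outcome change are taken over the same weeks, neither comes first. A participant whose back settles by natural course may report less disability, less hip pain and more confidence at the same visit. The regression then finds that hip changes explain disability changes, even if they did nothing to bring them about. The aim's wording invites the conclusion that hip pain, strength or confidence contributed to recovery, and the models cannot supply it.

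The adjustment set is a second weakness. A change score depends on where it started. Block 1 includes no starting level of the Quebec score or gait speed. For the window from 8 weeks to 6 months, the hip values named are the baseline ones, although that window starts at 8 weeks.

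**Working it through.** The documents give no effect size, correlation, SD or power for Aim 2, so there is no planned figure to reproduce. N = 180 (1:1) and two-sided 5% are from the plan. All effect sizes below are assumptions.

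**1. Same-window slope.** Let h and d be the standardised hip and outcome changes in one window, with e and e′ independent noise.

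- Hip drives outcome: d = 0.4h + √(1 − 0.4²)·e. Slope of d on h = 0.4.
- Outcome drives hip: h = 0.4d + √(1 − 0.4²)·e. Slope of d on h = 0.4.
- Shared cause u: h = √0.4·u + √0.6·e and d = √0.4·u + √0.6·e′. Covariance, and so slope, = 0.4.

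Adjusting for group leaves 177 degrees of freedom, so the expected t is about 0.4 × √177 / √(1 − 0.16) = 5.32 / 0.917 = 5.8, against a critical value of about 1.97. The test is almost always significant and gives the same estimate in all three cases.

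**2. Simulation** (N = 180, 3,000 runs per row, one hip measure, carry-over into the next window 0.3 where present). The lagged model regresses second-window outcome change on first-window hip change, adjusting for first-window outcome change and group. The reverse model swaps hip and outcome.

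| Assumed truth | Planned slope | Planned model significant, both windows | Lagged hip→outcome | Lagged outcome→hip |
|---|---|---|---|---|
| Hip drives outcome, carry-over | 0.40 | about 100% | 96% | 5% |
| Outcome drives hip, carry-over | 0.40 | about 100% | 4% | 97% |
| Shared cause, separate in each window | 0.40 | about 100% | 5% | 5% |
| Shared cause, persistent | 0.40 | about 100% | 98% | 98% |
| Hip drives outcome, no carry-over | 0.40 | about 100% | 5% | 5% |
| Outcome drives hip, no carry-over | 0.40 | about 100% | 5% | 5% |

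With all three hip measures only following disability, and the full Block 2 tested, the planned block was significant in 71–100% of trials across both windows (outcome reliability 0.8 to 1.0). At an assumed 144 completers (20% loss) it was 57–100%.

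**3. What a lagged model can do.** The table shows that it separates the two directions when effects carry over, and fails with a persistent shared cause or with effects completed within a window. Forward power at N = 180 is about 25%, 68% and 96% for carry-over of 0.1, 0.2 and 0.3. At 144 completers it is about 19%, 60% and 92%.

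The fuller version regresses the 6-month outcome on baseline-to-8-week hip changes, adjusting for baseline and 8-week outcome, baseline hip values and group (2,000 runs):

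- True hip effect acting at each visit (0.3 per measure): significant in 5.2% of runs at outcome reliability 1 and 8.1% at 0.9.
- No hip effect, hip measures only following disability (a similar model, 3,000 runs): about 5% and 8–11% at the same reliabilities, and 9–21% at reliability 0.8.
- No hip effect, persistent individual recovery slope: 98–99%.

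The first two results are nearly the same, so this model may not tell a real within-window effect from none.

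**4. Starting values.** Take equal variances and visit-to-visit correlation ρ, with correlation ρ² across two visits. The correlation of a change with its own starting value is −√((1 − ρ)/2). The correlation of second-window change with the baseline value is −ρ√((1 − ρ)/2).

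| Assumed ρ | Share of change variance tied to start-of-window value, (1 − ρ)/2 | Share of second-window change tied to baseline value, ρ²(1 − ρ)/2 |
|---|---|---|
| 0.5 | 25% | 6.25% |
| 0.7 | 15% | 7.35% |
| 0.9 | 5% | 4.05% |

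Block 1 leaves the first share unadjusted for the outcome. For second-window hip changes, baseline values capture only ρ² of what 8-week values would, that is 25%, 49% and 81% for these ρ.

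**The case against.** The strongest reply is that the hypothesis says only that the changes are associated, and the regressions test exactly that. This stands. In the simulations the hip measures are associated with disability, so a rejection rate near 100% is a correct rejection of no association. A reader might take it for a false-positive rate, but it is not one. The conflict lies between the aim's and the regressions' causal wording and an associational model.

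Four stronger readings are tempting, and the documents do not support them.

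- *Every model explicitly pairs same-window changes.* The plan gives no interval for the hip changes and none for the path analysis. Same-window is the natural reading, not a stated rule.
- *The three visits allow cause to be separated from consequence.* The assessments at baseline, 8 weeks and 6 months supply time order only. Working step 3 shows that a lagged model can miss a true contributor and endorse a false one.
- *These regressions will choose the target of the next trial.* The sentence about informing a follow-up study concerns the exploratory path analysis, which the plan itself expects to be underpowered.
- *Second-window change is mere drift because supervised treatment has ended.* The monthly calls in section 6 ask about exercise compliance and co-interventions, so real change may occur then.

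Two further replies have some force. Whether a change-score model should include the baseline outcome is debated, and it is a separate question from time order. The word baseline in Block 1 might also have been meant as the start of each window. If so, the plan should say so.

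**Conclusion.** The point holds in a limited form. On the natural reading, the Aim 2 regressions can show that hip changes and outcome changes move together. They cannot show that one contributed to the other: under the assumed correlation of 0.4, the slope and the roughly 100% rejection rate are the same for a contributor, a consequence and a shared cause. That indistinguishability does not depend on the value 0.4; the rejection rate does.

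The missing start-of-window values are a separate, correctable weakness. Under equal variances and ρ from 0.5 to 0.9, the unadjusted starting outcome value is tied to 5–25% of the variance of the change.

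Aim 1 is untouched. One of the trial's two stated aims is affected in how it is analysed and in what may be concluded, so the change should be made before analysis. It would go too far to say that Aim 2 could be answered causally by switching to a lagged model.

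**What to change.** 1. Report the same-window regressions as association only and draw no conclusion from them about what contributes to improvement. Align the wording of the aim and of the regressions' purpose with the hypothesis, and state the interval of every change score.
2. In each model, adjust for the outcome and the hip values at the start of that model's window: baseline values for baseline to 8 weeks, 8-week values for 8 weeks to 6 months.
3. Optionally pre-specify a lagged sensitivity analysis for each outcome: 6-month Quebec score or gait speed on baseline-to-8-week hip changes, adjusting for baseline and 8-week outcome, baseline hip values, group, age and sex, with its reverse-direction counterpart. State that it misses effects completed within one interval, is inflated by outcome measurement error and is not protected against a persistent common cause. Rest no causal statement on it.

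The cost is a few extra regressions and some rewording. No visits, measures or participants are added. The price is a more cautious Aim 2 conclusion.

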Pre-Entry Phase. Potential exclusions will be examined in two phases, first over the telephone using a structured questionnaire, then on-site with a standardized history and physical examination performed by a licensed physical therapist to validate the inclusion and exclusion criteria obtained by telephone. All of the on-site screening procedures will be performed after individuals have signed informed consent. All persons screened via phone or on-site will be assigned a number. If they are ineligible, a reason will be listed. They will also be asked if they would like to be contacted for future studies. If they verbally consent to future contact, their name, age, and contact information will be kept in a separate password protected folder under an encrypted UD server. All other documents will be shredded.

Assessments. All participants who are included based upon the screening criteria will receive identical pre-treatment assessments. A trained research assistant (masked to the intervention assignment) will administer outcome measures at baseline, prior to randomization. The same assessments will be made at the end of the intervention (i.e. 8 weeks post-enrollment) and 16 weeks post-treatment (i.e. 6 months post-enrollment).

Primary Outcome Measures

Self-Report Measures: These questionnaires evaluate self-perception:

1. **Pain-Related Disability:** The Quebec Back Pain Disability Scale²⁶, is reliable and valid questionnaire, which assesses low back pain-related disability. It has an established minimally clinically important change of 30%.²⁷
2. **Pain Severity:** Pain Thermometers (which have excellent reliability in older adults^{28,29}) will be used to assess pain severity in both the lumbar spine and hip at baseline, post-treatment, and 6 months.
3. **Patient-Reported Outcomes Measurement Information System (PROMIS)-29:**³⁰⁻³⁴ Developed by

the National Institutes of Health (NIH), the PROMIS-29 is a bank of questions for the clinical research community. It has demonstrated good reliability and construct validity for evaluating health-related quality-of-life. The PROMIS-29 profile includes questions assessing the following domains: physical function, anxiety, depression, fatigue, sleep disturbance, ability to participate in social roles and activities, pain interference, and pain intensity.

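### The Aim 2 models omit the outcome's own starting value and site; adding both costs three degrees of freedom and no new data

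*Combined protocol and SAP*

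**What the plan says.** Section 10 of the combined protocol and SAP (Data, Statistical Analysis, Aim 2) sets out sequential linear regressions. The outcomes are disability and physical "function, as measured by change in Quebec score and gait speed, respectively". Each is analysed over two intervals: baseline to 8 weeks, and 8 weeks to 6 months ("the second set from immediately post-treatment to 6 month follow up for Quebec scores", and likewise for gait speed).

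Block 1 is described as "covariates that are potential confounders (i.e. age and sex) as well as the baseline values of hip pain, hip strength and self-efficacy". Block 2 follows: "In the second block of each model will be the treatment group and change values for the predictors of hip pain, hip strength and self-efficacy".

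Aim 1, in the same section, treats site differently: "We will also control for site and sex as fixed effects since these are stratification factors in the randomization".

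The starting values will exist. Under Assessments in section 6, a masked assistant "will administer outcome measures at baseline, prior to randomization", and the same measures are repeated at 8 weeks and 6 months.

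**The concern.** The outcome is a change score, yet the level from which it starts is not in the model. Starting level usually predicts change, if only through regression to the mean. Leaving it out adds to the residual variance. If hip change is also related to the starting Quebec score or gait speed, it also shifts the hip-change coefficient.

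Site is a second gap. Randomisation balances treatment groups, but it does not balance who improves in hip pain, strength or confidence. If one site shows larger hip changes and larger outcome changes for reasons of its own, a pooled model without site reads part of that as an association between the two.

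Aim 2 asks what accounts for improvement, so its coefficients are the result. Covariate choice is its main protection against confounding.

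**Working it through.** **Inputs from the documents.** 180 participants, three recruitment areas, two-sided tests at 5%. The text does not say whether the 1% level for secondary outcomes applies to Aim 2; 5% is used here. No SD, effect size, correlation, dropout or power is given, so there is no stated figure to reproduce.

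**1. What the model contains.** Block 1 has 5 terms (age, sex, three baseline values). Block 2 has 4 (group, three changes). The total is 9, with no starting outcome and no site. No other text adds them: the baseline-imbalance sensitivity analyses concern the treatment comparison and list neither, and the path analysis mentions neither.

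**2. Precision.** Assume equal SD σ at both visits, start-to-follow-up correlation r, and a predictor unrelated to the starting value. The residual variance of change is 2σ²(1−r) without the starting value and σ²(1−r²) with it. The ratio is (1+r)/2.

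| r (assumed) | variance ratio | SE ratio | 180 unadjusted are worth |
|---|---|---|---|
| 0.3 | 0.65 | 0.806 | 117 |
| 0.5 | 0.75 | 0.866 | 135 |
| 0.7 | 0.85 | 0.922 | 153 |
| 0.9 | 0.95 | 0.975 | 171 |

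A simulation of the full 9-term model (180 participants, three sites, 3,000 replicates, standardised units) agrees. The SE falls from 0.095 to 0.083 at r = 0.5 and from 0.074 to 0.069 at r = 0.7. Power for a true coefficient of 0.2 rises from 54% to 66% and from 77% to 82%.

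**3. Bias when hip change is related to the starting outcome.** Same simulation, no true association, hip change depending on the starting outcome by 0.1 or 0.2 SD per SD:

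- r = 0.5: spurious coefficient 0.072 or 0.135 in size; false positives 13% or 32%.
- r = 0.7: 0.042 or 0.079; false positives 8–9% or 20%.

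The omitted coefficient is r−1, so bias should scale with 1−r. Check: 0.072 × 0.3/0.5 = 0.043 and 0.135 × 0.3/0.5 = 0.081, close to the 0.042 and 0.079 simulated. Adding the starting value brings bias to about 0 and false positives to 5–6%. That simulation makes follow-up depend linearly on the starting value, so the adjusted model is correct by construction.

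**4. Bias from measurement error.** A separate simulation used 160 complete cases, Quebec SD 14, true Quebec–hip-pain correlation 0.5 at baseline, reliabilities 0.85 and 0.75, improvement of about 30% of the starting score, and a true slope of 2 Quebec points per hip-pain point. It had 1,500 replicates and hip pain as the only hip predictor. The SE falls from 0.569 to 0.503 (12%), and power rises from 25.1% to 52.8%. Decomposing that rise:

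- An unbiased slope of 2 at SE 0.569 would have power Φ(2/0.569 − 1.96) = Φ(1.55) = 94%.
- Power of 25.1% therefore implies a mean estimate of (1.96 − 0.67) × 0.569 = 0.73. Power of 52.8% implies (1.96 + 0.07) × 0.503 = 1.02.
- Keeping 0.73 and changing only the SE gives Φ(0.73/0.503 − 1.96) = about 31%.

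So about 6 of the 28 percentage points come from the smaller SE; the rest is less attenuation. Three runs under similar assumptions gave mean estimates of 0.46, 0.66 and 1.00 without the starting value and 0.83, 1.05 and 1.24 with it. After the fix, (2 − 1.24)/2 = 38% to (2 − 0.83)/2 = 59% of the slope is still lost.

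**5. Site.** If site explains share q of both changes, fully aligned, the spurious correlation is about q. By Fisher's z, with standard error 1/√(180 − 8 − 3) = 1/13, false positives are 5.2% (q = 1%), 5.8% (2%), 10% (5%) and 26% (10%).

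In the standardised simulation with aligned site effects, the ranges being r = 0.5 to 0.7:

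- Site SD 0.1: about 5% as planned.
- Site SD 0.2: 9–12% as planned, 11–14% with the starting value alone, 5% with both terms.
- Site SD 0.2 plus the dependence in step 3 (0.2 SD): 46–50% as planned, 10–29% with either term alone, 5% with both.

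On the Quebec scale, aligned steps between sites of 4 Quebec points and 0.7 hip-pain points gave 11–12% as planned, 26% with the starting value alone and 6% with both. Steps of 3 and 0.5 gave 4.4% as planned and 4.3% with both.

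**6. Cost.** One term for the starting value and two for site. Residual df go from 180 − 1 − 9 = 170 to 167, and √(170/167) = 1.009.

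**The case against.** Several points against this have force.

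- **The 30% threshold.** A reader might infer that Quebec change scales with starting score because the protocol says of that scale, "It has an established minimally clinically important change of 30" percent. The documents do not support this. That figure is a threshold for interpreting change, not a model of expected change, and the gait-speed threshold is absolute (.07 m/sec). The case rests on regression to the mean and on the link between starting outcome and hip status.
- **Power.** A reader might take a rise from 25% to 53% as the price of imprecision. Step 4 shows it is mostly reduced attenuation, under assumptions that include proportional improvement. It cannot be cited as a precision gain.
- **Site confounding.** A reader might treat it as established. It is not. Different therapists and testers at each site is an inference, and the Interventions section says therapists will be trained for competence and reliability. In the larger Quebec-scale scenario the outer sites differ by 8 Quebec points and 1.4 hip-pain points, perfectly aligned.
- **A closed list.** The text's use of i.e. need not mean a closed list; exclusion criterion h uses it for examples. That stands as to intent. Even so, neither term is named anywhere for Aim 2.
- **A debated choice.** Conditioning a change score on an error-prone starting value, when the predictor is itself a non-randomised change, is arguable, and residual bias remains. But these models already condition on baseline hip values, so leaving out only the outcome's own starting level is hard to defend.
- **Coverage.** The Quebec-scale runs cover neither gait speed nor the second interval. The formula in step 2 and the standardised simulation are not tied to one scale.

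**Conclusion.** The omission is real and worth correcting. It costs precision: 13%, 8% or 3% in standard error at assumed correlations of 0.5, 0.7 or 0.9. It can also bias the hip-change slopes, with false positives of 8–32% where hip change depends on the starting outcome by 0.1–0.2 SD per SD. The site component is conditional: nothing to speak of at a 1–2% share of both changes, about 10% false positives at an aligned 5% share, and more beyond that.

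All of these sizes rest on assumed correlations, reliabilities and site differences, because the documents supply none. If change is unrelated to the starting value and sites behave alike, little is gained and about 1% in standard error is lost. Aim 1 does not depend on any of this. The point is a free improvement to an associational aim, not a fault in the treatment comparison.

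**What to change.** In section 10, Statistical Analysis, Aim 2, add to the description of block 1:

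> Block 1 of every model will also include the outcome's value (Quebec score or self-selected gait speed) at the start of the interval analysed, and site as a three-level factor. The starting value is the baseline measurement for baseline to 8 weeks, and the 8-week measurement for 8 weeks to 6 months.

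Add the two together. Under aligned site differences the starting value alone can raise false positives, because it sharpens the estimate without removing the site bias.

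Leave the rest of the blocks unchanged. The model without the two terms can be kept as a sensitivity analysis. The report should say that measurement error still attenuates the slopes, and that error shared by hip and outcome measures taken at the same visit is not removed.

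Cost: one sentence of text, three degrees of freedom, about 1% in standard error, and no new data.

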While there is longstanding expert agreement that LBP patients should be classified into subgroups prior to treatment,¹⁸⁻²⁰ no classification systems specific to the geriatric LBP population have been developed. There is strong evidence that classification approaches, where treatments are matched to the patient's limitations of that specific sub-group, can improve outcomes for patients undergoing physical therapy treatment for LBP.²¹⁻²⁴ To develop effective treatments, we must develop appropriate classification systems for older adults with chronic LBP.

Our preliminary data from the initial testing of the proposed hip-focused treatment among older adults with LBP suggest that this LBP subgroup may have a more favorable treatment response when the identified hip deficits, i.e. limitations, are also addressed. Therefore, the natural next step is to refine and further explore this hip-focused treatment for this newly identified at-risk subgroup (i.e. those with hip pain and weakness) through a well-controlled clinical trial. We propose a multi-site, single-blinded (i.e. examiners will not know participant treatment group assignment), randomized-controlled (i.e. participants will have an equal chance of getting 1 of 2 treatment plans), trial that advances findings from our previous study. We will recruit a total of 180 older adults with LBP of at least 3 months duration (i.e. chronic LBP) who are classified as members of the at-risk hip-spine subgroup. We will investigate whether a hip-focused treatment plan warrants further investigation as an approach to improve LBP and outcomes among older adults with chronic LBP. Manual therapy techniques will be used to address hip joint pain and progressive strengthening will be used to address hip weakness in one treatment group as compared to a LBP-focused treatment including manual therapy techniques to the low back region and low back muscle stretching. We will measure disability, LBP intensity, physical function (i.e. walking speed, chair rise performance, balance) and clinical hip deficits at baseline and after 8 weeks of intervention. We will also do a follow-up at 6 months (16 weeks post-treatment) to assess whether improvements hold from post-treatment to 4 months post-treatment.

The goals, i.e. specific aims, of the proposed research are to:

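### Aim 2's block test mixes treatment group with the three change scores, so its R-squared change does not measure what the hip and self-efficacy changes explain

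*Combined protocol and SAP*

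**What the plan says.** The Aim 2 hypothesis (Section 10, DATA) names three variables only: "Reductions in hip joint pain, increases in hip strength and increases in functional self-efficacy will be associated with improvements in LBP-related disability and physical function". The regressions are there to "determine the degree to which changes in hip pain, hip strength and functional self-efficacy explain changes in LBP-related disability and physical" function. Sequential multiple linear regression is to be "used to test if predictors of interest are related to the outcomes after adjusting for potential covariates", judged by the R-squared change as blocks are added.

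Block 1 holds age, sex and the baseline values of hip pain, hip strength and self-efficacy. For block 2 the plan states: "In the second block of each model will be the treatment group and change values for the predictors" of hip pain, hip strength and self-efficacy. The block result then acts as a gate: "If the block is significant, then the tests of the individual predictors will be examined".

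No step isolates the three changes from treatment. Section 5 words the specific aim more widely: "Determine what contributes to improvements in disability and physical function in this at-risk hip-spine subgroup".

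**The concern.** The question concerns three change scores; the test concerns those three plus treatment group. Aim 1 hypothesises a treatment effect on the same two outcome changes. Whatever part of that effect does not run through hip pain, hip strength or self-efficacy enters block 2's R-squared change. The better the treatment works by other routes, the less the block says about the three changes.

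A significant block, or a large R-squared change, could then be reported as evidence that the hip and self-efficacy changes explain recovery when it partly or wholly reflects allocation. The inflation persists when one of the changes really is associated with outcome. A lesser consequence is that the gate opens too easily and gives weaker protection over the three individual tests.

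**Working it through.** **Inputs from the documents.** 180 participants randomised 1:1 (Section 6); two-sided 5% level (Section 10); block 1 with 5 terms and block 2 with 4 terms, so 9 predictors (Section 10, Aim 2). The documents give no power, effect size or R-squared for Aim 2, so there is no planned figure to reproduce.

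**Assumptions.** n = 153 (180 × 0.85, a 15% loss), range 135 to 180; treatment effect d on the outcome change, in residual SD, from 0 to 0.5. In the simulations, unless stated: changes correlated 0.3 with each other and -0.4 with their baselines, residual SD 1, 8,000 runs.

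**Formula.** The block test is F = [(RSS1 - RSS2)/q] / [RSS2/(n - 10)], with q = 4 as written, or q = 3 if treatment is entered first and only the changes are tested. Treatment is randomised, so it is nearly uncorrelated with block 1. If no change score is related to outcome given treatment, the 4-df statistic has noncentrality λ = n·d²/4, while the 3-df statistic has noncentrality 0.

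At n = 153, residual df = 143:
- d = 0.3: λ = 153 × 0.09/4 = 3.44
- d = 0.42: λ = 153 × 0.1764/4 = 6.75
- d = 0.5: λ = 153 × 0.25/4 = 9.56

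**Result 1: all three changes null, nothing mediated. Chance that the block is significant.**

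| d | 4-df, formula | 4-df, simulated | 3-df, simulated |
|---|---|---|---|
| 0 | 5.0% | 5.2% | about 5% |
| 0.1 | 6.9% | 6.6% | about 5% |
| 0.2 | 13.6% | 13.9% | about 5% |
| 0.3 | 26.9% | 25.8% | about 5% |
| 0.42 | 50.8% | 48.1% | about 5% |
| 0.5 | 67.7% | 66.4% | about 5% |

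The 3-df column lies between 4.7% and 5.4% throughout. For n from 135 to 180 the 4-df rate is 23-31%, 43-57% and 60-74% at d = 0.3, 0.42 and 0.5. The block is significant with no single change at p < 0.05 in 17.5%, 37.3% and 54.0% of runs, against 0.4% for the 3-df block.

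**Result 2: one change truly associated (coefficient 0.3), treatment effect unmediated. Mean R-squared change.**

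| d | As written | Changes alone | Excess |
|---|---|---|---|
| 0.3 | 0.108 | 0.083 | 0.025 |
| 0.42 | 0.124 | 0.081 | 0.043 |
| 0.5 | 0.138 | 0.080 | 0.058 |

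With a 0.42 SD effect half mediated through the changes (6,000 runs), the figures are 0.127 against 0.083.

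**Result 3: multiplicity.** The chance of passing the gate and flagging a null change, at d = 0.3 to 0.5:
- all three null: 8.3-12.4% as written, 4.4-4.8% with the 3-df gate;
- one change associated, coefficient 0.3: 9.0-9.5% against 8.8-9.2%;
- one change associated, coefficient 0.2: 8.0-9.6% against 7.2-8.1%, at most 1.6 points apart;
- one change associated, coefficient 0.4: no difference.

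**The case against.** **A significant block is a step, not the conclusion.** The plan goes on to the individual predictors, whose coefficients are adjusted for treatment and keep their 5% level. In most of the wrongly significant blocks no individual change is significant, so the next step would show this. That stands, and it limits the harm to the block test, its R-squared change and the gate. It does not restore the R-squared change, which is the only measure of degree these regressions offer.

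**The null in Result 1 is conditional on treatment.** If treatment moves both a hip measure and the outcome, the two are associated marginally, and the hypothesis says only associated. That also stands: a null in the marginal sense as well requires that treatment does not shift the changes.

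**Nothing mediated is the extreme case.** The HIP+ arm targets hip pain and strength directly, so some mediation is likely. The half-mediated case still shows R-squared inflation, but the chance of passing the gate and flagging any change differs little there (69% against 66%).

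**The later interval may be unaffected.** Section 5 describes the 6-month visit as a check to "assess whether improvements hold from post-treatment to 4 months post-treatment". If the arms do not diverge further, d for that change is small and the block rate is 5-14% at d = 0 to 0.2.

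**Treatment belongs under the wider aim.** It fits the Section 5 wording, but the hypothesis and stated purpose in Section 10 name the three changes.

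**The exploratory path analysis is no substitute.** It asks whether baseline hip measures act through their changes, and the plan itself expects it to be underpowered.

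**Conclusion.** The concern holds. As written, block 2 is a joint test of treatment and three change scores, and neither its p-value nor its R-squared change answers the Aim 2 question. The main consequence is an R-squared change overstated by 0.025 to 0.058 with one associated change and an unmediated effect of 0.3 to 0.5 SD. In the worst case, with no change related to outcome given treatment, the block is significant in 26% to 66% of trials. Loss of multiplicity protection is secondary.

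These sizes rest on assumed effects, correlations and dropout; with no treatment effect the block keeps its 5% level. Aim 1 is untouched, and no individual coefficient or p-value changes. This should be corrected because Aim 2 is a stated specific aim, but it does not threaten the primary analysis.

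**What to change.** Enter treatment group in block 1, or as its own step before the change scores. Test the three changes as a 3-df block, use that test as the gate, and report its R-squared change as the Aim 2 quantity, described as a within-arm association. Report the 4-df R-squared change beside it, labelled as treatment plus changes. Settle this before unblinded analysis.

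Only the analysis wording changes, since every variable is already collected. The real cost is that variance shared by treatment and the changes is credited to treatment:
- **Fully mediated** (coefficient 0.15 for each change, 1 SD shift in each, changes uncorrelated with each other and with baseline, 5,000 runs): R-squared change falls from 0.124 to 0.075, block power from 92% to 73%, and power to pass the gate and flag a predictor from 79% to 72%.
- **Fully mediated, changes correlated 0.3:** block power falls from 96% to 86% (1 SD shift) or from 88% to 86% (0.5 SD shift).
- **One associated change (coefficient 0.3), effect unmediated:** the chance of passing the gate and flagging it falls from 80% to 75% at d = 0.3 and from 84% to 76% at d = 0.5, because the treatment effect no longer helps to open the gate. At d = 0 it rises from 72% to 76%.

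Reporting both quantities keeps the combined result available to readers who want it.
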